### **Frequency of Monitoring**

The PI will review Study Reports (e.g., acquired data and available safety information) on a weekly basis and will share safety and progress reports with all co-Investigators on a weekly basis.

Formal interim monitoring will be performed by the PI annually. For both continuous and interim monitoring, safety occurrences will be evaluated for severity, attribution, and possible trends.

- All adverse events that are anticipated or described in the informed consent form will be logged appropriately and reported to the IRB on at least an annual basis (e.g., at continuing review).
- Any Unanticipated Problems or unexpected “Serious Adverse Events” (SAEs) related to the study intervention and affecting the risk/benefit profile of the study, will be reported to the IRB promptly, and, in all cases, within 10 business days of discovery.
- Unplanned and non-emergent deviations from the IRB approved protocol will be logged, include a corrective action plan, if necessary, and be reported to the IRB annually at continuing review; all planned deviations will be submitted as a Change in Research to the IRB for approval and prior to implementation. All other event reporting requirements will be followed and all necessary parties will be notified of events/problems encountered in the study and/or changes in research, in accordance with all applicable regulations and guidelines.

Interim monitoring findings and corrective actions will be summarized in a report to be retained in the regulatory file.

Study report outline (Interim or Annual Reports): The study team will generate Study Reports and will provide information on accrual rates, retention, adverse, and severe adverse events to track the study’s progress. Study Report tables will be generated using aggregate data (not by group assignment).

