**Exploring moderating factors.** We will explore the moderating effect of fathers' resident status, partner relationship quality, and caregiver conflict from perspectives of both parents on the study's outcomes given that each of these may influence fathers' access and experience with infant engagement, as well as other background factors. These findings will inform sampling decisions and future research questions for a larger trial. We will also explore how infant sex as a biological variable might impact father engagement; however, this is not supported by past work in this area.

We will also explore differences among intervention and usual care control arms for each maternal and infant outcome between baseline and follow-up.

b. Early stopping rules.

This study may be stopped prior to its completion if:

- (1) participants experience (adverse events) AEs or severe AEs (SAEs) that are felt to be related to study participation, at which point consideration will be given to temporarily or permanently suspending study activities and/or enrollment. This decision would be made in consultation with the study's IRB and sponsor (NICHD);
- (2) difficulty in study recruitment or retention will significantly impact the ability to evaluate the study endpoints. The investigators will consult with the study monitors to assess the impact of significant data loss due to problems in recruitment, retention, or data collection;
- (3) any new information becomes available during the trial that necessitates stopping the trial; or
- (4) other situations occur that might warrant stopping the trial.

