## 8. Risks

a. Medical risks, listing all procedures, their major and minor risks and expected frequency.

There are no significant medical risks involved in this study. This study falls in the category of "research not involving greater than minimal risk," described by federal regulations as "the risks of harm anticipated in the proposed research are not greater considering probability and magnitude, than those ordinarily encountered in daily life or during the performance of routine physical or psychological examinations or tests." Research in this category includes: "...confidential survey research that collects identifying information, with or without sensitive information."

This study will involve the use of surveys and receipt of text messages. All participants will be informed

that participation in the study is completely voluntary and will be reminded that they can decide not to answer any question on the brief survey and that they can stop participating at any time. Potential risks for participants who participate in this study include distress related to the research study (e.g., personal nature of questions asked). While the study will attempt to preserve patient confidentiality, there is potential for breaches of confidentiality, but minuscule given the limited number of personnel with access to participant information. It is also possible that by promoting father engagement, the intervention could increase friction between parents and/or other key caregivers that could also result in distress and/or conflict. However, past perinatal research focused on father involvement suggest that programs to enhance maternal-paternal relationships actually improve maternal mental health outcomes and has not found harms associated with father-mother relationships as a result of greater father involvement. We have developed a monitoring plan to assess for these issues and resources to refer participants as needed.

b. Steps taken to minimize the risks.

Human subject approval has been granted for prior formative work and pilot feasibility testing of this research protocol by the Johns Hopkins institutional review (IRB00117690) that has informed the current protocol. Significant attempts will be made to minimize risks to participants.

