- An explanation of the basis for determining that the adverse event, incident, experience, or outcome represents an unanticipated problem;
- A description of any changes to the protocol or other corrective actions that have been taken or are proposed in response to the unanticipated problem.

To satisfy the requirement for prompt reporting, unanticipated problems will be reported using the following timeline:

- Unanticipated problems that are serious adverse events will be reported to the IRB and sponsor (NICHD) within 7 days of the investigator becoming aware of the event.

**AE Reporting of Non-Investigational New Drug (IND) Studies:** SAEs that are unanticipated, serious, and possibly related to the study intervention will be reported to the IRB and sponsor (NICHD) in accordance with requirements.

- Unexpected fatal or life-threatening SAEs will be reported to the IRB and the sponsor (NICHD) within 3 days of the PI becoming aware of the event. Other serious and unexpected AEs related to the intervention will be reported within 7 days.
- Anticipated or other SAEs will be handled in a less urgent manner but will be reported to the IRB and sponsor (NICHD), and other oversight organizations in accordance with their requirements.

All other AEs documented during the course of the trial will be reported to the sponsor (NICHD) on an annual basis by way of inclusion in the annual report and in the annual AE summary which will also be provided to the IRB.

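### No report planned during the trial can show an excess of parental conflict in the Text4Father arm: Study Report tables are pooled and omit the interim-text answers

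*Combined protocol and SAP*

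**What the plan says.** Section 8a (Medical risks) lists three kinds of risk. Distress from survey questions and breach of confidentiality come from taking part in research. The third comes from the intervention: "the intervention could increase friction between parents and/or other key caregivers that could also result in distress and/or conflict". Section 8b then describes monitoring by short text queries about the relationship with the partner, the relationship with other caregivers, and the need for support.

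Under Frequency of Monitoring, the Study Reports "will provide information on accrual rates, retention, adverse, and severe adverse events". The query answers are not among the listed contents. On layout, the plan says "Study Report tables will be generated using aggregate data (not by group assignment").

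Some safety review is not pooled. Under the same heading, "For both continuous and interim monitoring, safety occurrences will be evaluated for severity, attribution, and possible trends". The Review Table has SAEs reviewed at each occurrence by the investigators and the sponsor. The reporting timelines that follow it add: "Unanticipated problems that are serious adverse events will be reported to the IRB and sponsor (NICHD) within 7 days". Section 7b allows the study to be stopped if "participants experience (adverse events) AEs or severe AEs (SAEs) that are felt to be related to study participation", in consultation with the IRB and sponsor; it sets no threshold and no comparison of arms.

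At the end, the Aim 3 models compare each study outcome by arm. The Measures Table counts cooperative coparenting and partner relationship quality as outcomes. It lists caregiver conflict only as a moderator.

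**The concern.** Strain between partners can arise in either arm around a birth; the protocol's own query texts describe becoming a parent as potentially stressful. For a harm that also occurs without the intervention, the useful evidence is an excess over usual care. A pooled count has nothing to be judged against, because the documents state no expected rate of conflict or distress.

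Pooling often protects a blind, but Section 4c says the study is not blinded, and no other reason is given for it here. If Text4Father raised conflict moderately, with each case unremarkable on its own, no table described for use during the trial would reveal it. The stopping provision would then depend on judging each event separately. The relatedness criteria in Section 8 (timing, abatement on stopping, recurrence on re-challenge) discriminate poorly for gradual relationship strain during about seven months of twice-weekly texts.

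**Working it through.** The plan states no rate, threshold or power for harm, so there is no figure of its own to reproduce. The check has three parts.

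**1. Could the planned tables contain the signal?** Study Reports cover accrual, retention, AEs and SAEs. The AE definition covers an unfavourable diagnosis, sign, symptom, syndrome or disease. A 'worse' answer about a relationship does not clearly fit it. Splitting only the AE tables by arm might therefore still miss conflict; the query answers need their own rows.

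**2. Is there a comparator?** The documents disagree.
- Section 4, Control Groups: the usual care arm receives the three interim texts, at 2, 4 and 6 months.
- Section 4b: all fathers and mothers receive them.
- Section 8b: between visits, mothers in both arms are queried, but among fathers only those in the intervention arm.

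Under the Section 8b wording there are no interim answers from usual-care fathers, and only mothers can be compared.

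**3. What does pooling lose?** Inputs: 60 couples per arm (Section 7a), and 48 per arm after the 20% loss stated there (60 × 0.80 = 48). The rates of a 'worse' answer are assumptions, pC in usual care and pT in Text4Father, for one parent type at a time.

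Pooled expected count = 60·pC + 60·pT, with SD = √[60·pC(1−pC) + 60·pT(1−pT)].
- 10% against 20%: 6 + 12 = 18; SD = √(5.4 + 9.6) = 3.87.
- 15% in both arms: 9 + 9 = 18; SD = √(7.65 + 7.65) = 3.91.

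The means are equal and the spreads almost equal, so the pooled count carries essentially no information about a difference between arms.

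For a by-arm table, two quantities follow. P(higher) is the exact binomial probability that the intervention count exceeds the control count with 60 per arm. Power uses the arcsine approximation, two-sided 5%: power ≈ Φ(h·√(n/2) − 1.96), where h = 2·arcsin√pT − 2·arcsin√pC. For 10% against 20%, h = 0.9273 − 0.6435 = 0.2838. At n = 60, 0.2838 × √30 = 1.554, and Φ(1.554 − 1.96) = 0.34.

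| Assumed rates (pC, pT) | Expected by arm, 60 each | Pooled of 120 | P(higher) | Power, 60 per arm | Power, 48 per arm |
|---|---|---|---|---|---|
| 5%, 10% | 3, 6 | 9 (7.5%) | 0.81 | 0.18 | 0.15 |
| 10%, 20% | 6, 12 | 18 (15%) | 0.92 | 0.34 | 0.28 |
| 10%, 25% | 6, 15 | 21 (17.5%) | 0.98 | 0.60 | 0.51 |
| 10%, 30% | 6, 18 | 24 (20%) | 0.997 | 0.81 | 0.71 |
| 20%, 40% | 12, 24 | 36 (30%) | 0.99 | 0.68 | 0.58 |

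With 15% in both arms, P(higher) is about 0.45 (ties make up the rest of the half). A merely higher intervention count is thus weak evidence, and the size of the gap must be weighed. The 60-per-arm columns assume that everyone has answered; a look partway through accrual would have less.

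**The case against.** The sponsor can fairly say that this is a minimal-risk texting study with several safeguards. A 'worse', 'yes' or 'unsure' answer brings that person contact details and resources. Each safety occurrence is assessed for attribution. Because the study is open and the principal investigator reviews data weekly, nothing prevents someone from noticing a difference between arms. Section 8a also reports that past perinatal work found no such harm. An annual table is slow against seven months' participation, and most realistic differences would not reach significance.

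Much of this stands, and it limits the point. A reader might infer that all safety reporting is pooled. The documents do not support that: the sentence covers Study Report tables, while SAEs and unanticipated problems are reported one by one. A reader might also infer that harm from the intervention could not be seen at all, or could not stop the study. That too goes too far: a single event judged related can bring Section 7b into play, and the final by-arm comparison of coparenting and relationship quality can show related harm. Nor would splitting the existing tables alone expose conflict, since the query answers are not in them.

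What the objection does not remove is narrower. Individual referral and case review do not measure an excess over usual care, and informal awareness of allocation is not a specified comparison.

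**Conclusion.** The point holds in this limited form: during the trial, no planned report sets the arms side by side on the one harm the protocol ties to the intervention. Two features combine to cause this, the explicit pooling rule and the absence of query answers from the listed contents. The first is a stated rule, not just missing detail.

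The practical size is modest. At an assumed doubling from 10% to 20%, the pooled table shows nothing, while a by-arm table would show the intervention count higher about nine times in ten. That is material for judgement, not for a test. All rates are assumptions and the documents cannot narrow them. For fathers, the conclusion also depends on usual-care fathers being queried, which the documents leave contradictory. It is a low-cost improvement worth considering.

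**What to change.** Keep the pooled Study Report tables for the investigators. Add to the annual report already planned for the IRB and sponsor a closed by-arm table with:
- AEs and SAEs;
- 'worse', 'yes' and 'unsure' answers at each interim query;
- fathers and mothers in separate rows, with the number responding in each arm as denominator.

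It should be prepared by someone not involved in outcome assessment, and the plan should say that it is descriptive.

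Reconcile Section 8b with Control Groups and Section 4b on which fathers receive the interim queries, and state in the plan which comparison (fathers, mothers or both) is then possible.

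The cost is one extra table from data already collected. The downsides are that one person sees by-arm safety counts early, though no efficacy outcomes, and that small counts could be over-read. Showing denominators and stating the low power, about 0.34 at the assumed 10% against 20% with 60 per arm, guards against the second.

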### **REVIEW TABLE**

Data type	Frequency of review	Reviewer
Subject accrual (including compliance with protocol enrollment criteria)	Quarterly	Investigators
Status of all enrolled subjects, as of date of reporting	Semi-annually	Investigators
Adherence data regarding study visits and intervention	Quarterly	Investigators
AEs and rates (including out-of-range lab values)	Semi-annually	Investigators
SAEs	Per occurrence	Investigators, Sponsor (NICHD)

c. Plan for reporting unanticipated problems or study deviations.

Any unanticipated problems or adverse events will be reported to the IRB immediately. Deviations from the original study protocol will be requested through a change in research request.

Collection and Reporting. For this study, the following standard AE definitions will be used:

**Adverse Event (AE):** Any unfavorable and unintended diagnosis, sign (including an abnormal laboratory finding), symptom, syndrome, or disease which either occurs during the study, having been absent at baseline, or if present at baseline, appears to worsen. All adverse events will be recorded.

**Unanticipated Problems (UP):** Unanticipated problems involve risks to subjects or others include, in general, any incident, experience, or outcome that meets all of the following criteria:

- Unexpected in terms of nature, severity, or frequency given (a) the research procedures that are described in the protocol-related documents, such as the IRB-approved research protocol and informed consent document; and (b) the characteristics of the subject population being studied;
- Related or possibly related to participation in the research (“possibly related” means there is a reasonable possibility that the incident, experience, or outcome may have been caused by the procedures involved in the research); and
- Suggests that the research places subjects or others at a greater risk of harm (including physical, psychological, economic, or social harm) than was previously known or recognized.

Unanticipated problems will be recorded in the data collection system throughout the study.

**Serious Adverse Event (SAE):** Any AE that results in any of the following outcomes:

- Death
- Life-threatening event
- Event requiring inpatient hospitalization or prolongation of existing hospitalization
- Persistent or significant disability/incapacity
- An important medical event based upon appropriate medical judgment

All serious adverse events will be recorded.

Characteristics of an AE:

**Relationship to Study Intervention:** To assess relationship of an event to study intervention, the following guidelines will be used:

1. Related (Possible, Probable, Definite)

- a. The event is known to occur with the study intervention.
- b. There is a temporal relationship between the intervention and event onset.
- c. The event abates when the intervention is discontinued.
- d. The event reappears upon a re-challenge with the intervention.

2. Not Related (Unlikely, Not Related)

- a. There is no temporal relationship between the intervention and event onset.
- b. An alternate etiology has been established.

**Expectedness of SAEs:** The PI will be responsible for determining whether an SAE is expected or unexpected. An adverse event will be considered unexpected if the nature, severity, or frequency of the event is not consistent with the risk information previously described for the intervention.

**Severity of Event:** We will use the following scale to grade adverse events:

1. Mild: no intervention required; no impact on activities of daily living (ADL)
2. Moderate: minimal, local, or non-invasive intervention indicated; moderate impact on ADL
3. Severe: significant symptoms requiring invasive intervention; subject seeks medical attention, needs major assistance with ADL

Reporting Procedures: The anticipated potential adversity inherent in participation is limited to those

situations described above and will be addressed by the timely intervention of research staff members skilled in risk assessment and mandatory reporting requirements.

**Reporting Procedure for Serious Unanticipated Adverse Events:** In the event of an unanticipated serious adverse event occurring during study enrollment, the project PI will ensure that these events are reported to the IRB and sponsor (NICHD) within 7 days by phone, fax, and/or email. Incidents or events that meet the criteria for unanticipated problems require the creation and completion of an unanticipated problem report form. The following information will be included when reporting an adverse event, or any other incident, experience, or outcome as an unanticipated problem to the IRB:

- Appropriate identifying information for the research protocol, such as the title, investigator's name, and the IRB project number;
- A detailed description of the adverse event, incident, experience, or outcome;
- An explanation of the basis for determining that the adverse event, incident, experience, or outcome represents an unanticipated problem;
- A description of any changes to the protocol or other corrective actions that have been taken or are proposed in response to the unanticipated problem.

To satisfy the requirement for prompt reporting, unanticipated problems will be reported using the following timeline:

- Unanticipated problems that are serious adverse events will be reported to the IRB and sponsor (NICHD) within 7 days of the investigator becoming aware of the event.

**AE Reporting of Non-Investigational New Drug (IND) Studies:** SAEs that are unanticipated, serious, and possibly related to the study intervention will be reported to the IRB and sponsor (NICHD) in accordance with requirements.

- Unexpected fatal or life-threatening SAEs will be reported to the IRB and the sponsor (NICHD) within 3 days of the PI becoming aware of the event. Other serious and unexpected AEs related to the intervention will be reported within 7 days.
- Anticipated or other SAEs will be handled in a less urgent manner but will be reported to the IRB and sponsor (NICHD), and other oversight organizations in accordance with their requirements.

All other AEs documented during the course of the trial will be reported to the sponsor (NICHD) on an annual basis by way of inclusion in the annual report and in the annual AE summary which will also be provided to the IRB.

### **Data Sharing Plan (as required per NIH guidance)**

**Data Access and Security.** Quantitative survey data will be de-identified (all sensitive identifiable or potentially identifiable information will be protected). Data will be stored on an enterprise network encrypted secure server for direct access at JH's institutional OneDrive, which has HIPAA security levels, as a secondary location for data that has removed non-essential direct identifiers. No data will be used and/or released without prior approval by the principal investigator. Any activity through this site is log accessible to the editor. Any material with personal health information (i.e., consent forms with identifiers) will be kept separately from data in a key-locked filing cabinet in a secure/private office space during the project period and destroyed immediately after the project period. Appropriate consents for deposition of survey data into public databases for future use will be obtained through the formal consent process.

**Data Documentation.** The research team will develop data documentation materials that describe the method of data collection, data codebook/data dictionary, and other documentation of the study variables that will be useful during later access by the study team and with the final archival files.

**Data Archiving and Long-term Preservation.** The final version of the collected dataset will be made available within thirty (30) months after the end of the data collection. For data underlying scientific publication, the data will be made available to coincide with publication of the paper, unless the dataset is already available via a release or sharing mechanism. At a minimum, release of the dataset will consist of a machine-readable version of the data tables shown in the paper.

Datasets 1 and 2 (see table below) will be preserved and made accessible along with the data codebook and other relevant documentation via the chosen repository. We will make the data available through open access (Open Inter-university Consortium for Political and Social Research (ICPSR)) if possible. JHU School of Medicine will review the disclosure protection of the de-identified datasets. If they conclude that the risk of disclosure is too great for public access, then ICPSR's Traditional Restricted Data or Physical Data Enclave will be used for some or all of the data, with restricted access solely to approved researchers. The project may consider the SOM's fee-based service for de-identifying the dataset. Open ICPSR is a research data-sharing service of the Inter-university Consortium for Political and Social Research. ICPSR is a leading resource in the field for social science, government, and public health data and has a nearly 50-year track record for preserving and making data available. Through ICPSR, whether using the open archive or the restricted options, these particular research datasets and associated documentation will be preserved and made accessible to researchers in the social sciences, public health, medical communities, and beyond. JHU may provide a restricted access data repository at that time which we may consider as an alternative, as well as any repositories recommended by NIH for this grant.

Datasets (Input and/or Output)		Format(s)	Est size/amount	Shared?
1	Quantitative acceptability of technology usability, acceptance, and satisfaction data among father participants assigned to Text4Father	CSV	60 respondents	Yes, de-identified or with restricted access only
2	Quantitative baseline and follow-up data of father and mother participants in all arms	CSV	Baseline: 120 respondents Follow-up: 96 respondents	Yes, de-identified or with restricted access only

